2. AIM/ OBJECTIVES

The study aims to compare the doses of 10 versus 25 milligrams of Empagliflozin among diabetic patients with Anterior STEMI with reduced LVEF who underwent PPCI regarding MACE and LV remodeling for 6 months duration.

3. Methodology:

- **Type of Study:** a prospective clinical trial.
- **Study Setting:** Patients presenting to Ain shams university hospitals
- **Study Population:** anterior STEMI patients
- **Study Period:** 6 months
- **Sample Size:** Patients diagnosed with anterior STEMI in the ER fulfilling the inclusion criteria. (200 patients) divided into two groups the first will receive 10 mg of Empagliflozin and the other will receive 25 mg.
- **Ethical considerations:**
The clinical research study will be conducted in accordance with the current policies, requirements, and regulations of Ain Shams University. Information will be recorded in an appropriate manner to ensure that potential subjects or their authorized representatives are fully aware of the nature and objectives of the clinical study, and the potential risks and benefits of participating in the study. Written informed consent will be obtained from each patient or their authorized representative, prior to any study procedures being carried out.
- **Inclusion Criteria:**

- 1- Diabetic patients with anterior STEMI with reduced LVEF who underwent PPCI with successful revascularization and resulting into TIMI III flow and who are receiving SGLTi for the first time.

Exclusion Criteria:

- 1- patients who did not undergo primary PCI, those treated medically or had thrombolysis
- 2- Non diabetic patient.
- 3- Diabetic patient already on SGLTi
- 4- STEMIs other than anterior.
- 5- NSTEMI patients.
- 6- Patients having valvular heart diseases.
- 7- Patients having renal impairment.
- 8- Patients with LV myopathies of non-ischemic origin.

4. Study Tools:

A- history taking: including

- a- personal history" name, age, marital status and special habits of medical importance e.g smoking and alcohol consumption "
- b- past history with special comment on diabetes and other comorbidities e.g hypertension, CKD and dyslipidemia

- c- History of present illness with special comment on pain to door interval.
- d- Positive family history.
- e- Drug history: and to make sure whether patients are receiving SGLTi or not.

B- Examination:

- 1- General examination: including vital signs and complexion.
- 2- Local examination including heart and chest auscultation.

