C- ECG: all patients will have 12 lead surface ECG at start of the study and during follow up.

D- Echocardiographic Assessment:

1- Standard transthoracic 2D echocardiographic examination:

Standard 2D echocardiography will be performed using GE vivid E70 echocardiography machine; the whole study will be ECG gated in supine or left lateral position. Standard images will be obtained in the parasternal (long- and short-axis views) and apical (2, 3, 4, and 5-chamber images) views. Standard 2D and color Doppler data, triggered to the QRS complex, will be saved in cine-loop format.

M-mode, 2D, TDI as well as pulsed and continuous Doppler flow across the different heart valves in all the standard views will be done according to the recommendations of the American Society of Echocardiography (7).

Heart failure with reduced ejection fraction (HFrEF) was defined as EF less than 40% , Also referred to as systolic HF. Randomized controlled trials have mainly enrolled patients with HFrEF, and it is only in these patients that efficacious therapies have been demonstrated to date.(8)

The definition of left ventricular remodeling using cardiac magnetic resonance following ST-elevation myocardial infarction is highly variable, among studies including highly selected patients. The most frequent left ventricular remodeling criterion were a 20% increase in end-diastolic volumes or a 15% increase in end-systolic volumes.(9)

A composite cut-off value of a 12% to 15% increase in end-systolic volume and a 12% to 20% increase in end-diastolic volume using a follow-up cardiac magnetic resonance imaging 1 to 3 months after myocardial infarction might be proposed as a consensual cut-off for defining adverse left ventricular remodeling.(9)

The following measurements will be focused on and recorded:

1- Assessment of LV systolic function :

By applying M-Mode modality to LV in parasternal long axis view, we will measure LV end-diastolic diameter (EDD), LV end-systolic diameter (ESD), IVS and PWT in both systole and diastole LVEF and FS. Also estimation of EF by Simpson biplane method and 2D will be done.

2- LA dimension measurement:

Left Atrial dimensions and aorta: The anteroposterior diameter of the left atrium will be measured in the parasternal long-axis view using M mode perpendicular to the aortic root long axis at the level of the aortic sinuses by using the leading-edge to leading-edge convention.

3- Wall motion abnormalities:

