The software then generates a region-of-interest (ROI) to include the entire myocardial thickness. The width of the ROI can be manually adjusted as required. Care should be taken to avoid including bright, echogenic pericardium in the ROI.

The software then divides the LV myocardium into six segments and generates segmental and global longitudinal strain. As the myocardium usually shortens in the longitudinal direction during systole, the longitudinal strain is displayed below the baseline.

From these curves, peak systolic longitudinal strain is recorded for each of the myocardial segments. The strain values for all the segments are recorded and averaged to obtain the global longitudinal strain (GLS). A topographic representation of the regional and global longitudinal strain of all 17 analyzed segments (Bull's eye configuration) is then automatically generated.

F- 2D Speckle Tracking Echocardiography of the left Atrial Phasic functions (apical four chamber view and apical two chamber view) Parameters:

- Left Atrial Strain during Reservoir phase (LASr): Reflects the left atrium's ability to store blood during ventricular systole.
- Left Atrial Strain during Conduit phase (LAScd): Assesses the passive filling of the left ventricle during early diastole.
- Left Atrial Strain during Contraction phase (LASct): Evaluates the active contraction of the left atrium during late diastole.
- Left atrial maximum volume (LAVmax): It is measured just before the mitral valve opens, at the end of left ventricular systole.

G- Major adverse cardiac events (MACE): composite point of death, repeated hospitalization, re-infarction and new onset heart failure will be observed for six months post catheterization and initiation of SGLTi.

H- Follow up: patients will be followed up for 6 months regarding symptoms and MACE. All echocardiographic study parameters will be repeated at the end of the study period.

5-Statistical Analysis:

All data will be statistically analyzed to compare results in different time (day one then 6 months later)

6. References:

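### The one comparison stated in Section 5 is day one versus 6 months for all data; it names no dose group, although the aim is 10 mg versus 25 mg, and it cannot be applied to MACE

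*Protocol*

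**What the plan says.** Section 2 sets a between-dose question: "The study aims to compare the doses of 10 versus 25 milligrams of Empagliflozin", with MACE and left ventricular remodeling as the outcomes over 6 months. Under Sample Size, Section 3 gives 200 patients, "divided into two groups the first will receive 10 mg of Empagliflozin and the other will receive 25 mg". The split between the groups is not stated.

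Section 5 is a single sentence: "All data will be statistically analyzed to compare results in different time (day one then 6 months later". It mentions neither dose nor group, and no other part of the protocol states a between-dose analysis.

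Three items in Section 4 bear on how that sentence can be used:

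- Item D gives, as background, the usual criteria for remodeling as a rise in volume: "a 20% increase in end-diastolic volumes or a 15% increase in end-systolic volumes".
- Item G says that MACE "will be observed for six months post catheterization and initiation of SGLTi".
- Item H says "All echocardiographic study parameters will be repeated at the end of the study period".

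**The concern.** The contrast in the aim is between doses; the contrast in the analysis section is between times. Both groups receive empagliflozin. A change from day one to 6 months therefore mixes drug effect, recovery after the infarct and the effect of revascularization, and by itself carries no information on whether 25 mg differs from 10 mg.

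An analyst who follows Section 5 to the letter has two options. Pooling the groups gives an average change and no dose estimate. Testing each group separately gives two p-values, and the tempting step is to read a dose effect into one being below 0.05 and the other above it. That step is not a test of the dose difference and can suggest one where none exists.

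MACE is one of the two outcomes in the aim and falls under a rule that covers all data, yet it has no day-one measurement to compare with.

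**Working it through.** **1. The contrasts side by side**

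| Place | Contrast | Outcomes |
|---|---|---|
| Section 2 | 10 mg versus 25 mg | MACE, LV remodeling |
| Section 3, Sample Size | two dose groups, 200 patients | – |
| Section 5 | day one versus 6 months | all data |

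The first two rows agree with each other. The third names a different contrast.

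**2. Does the Section 5 contrast fit each outcome?**

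- *Echocardiographic measures.* They are taken on day one and repeated at the end, so a change can be computed for each patient. The further step, comparing that change or the 6-month value between doses, is not stated.
- *MACE.* Events are counted only after catheterization and the start of the drug. There is no day-one value. If one is set to zero for everyone, the comparison asks only whether events occurred, which is not a question about dose.

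**3. How often separate within-group tests mislead**

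The protocol gives no figure to reproduce here. Assumptions: 100 patients per group, two-sided 5% level, normal approximation, and the same true change d (in SDs of change) in both groups, so that there is no dose difference.

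The probability that one group's change is significant is

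p = 1 − Φ(1.96 − d√100) + Φ(−1.96 − d√100).

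The groups are independent, so the probability that exactly one is significant is 2p(1 − p).

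For d = 0.3: d√100 = 3, p = 1 − Φ(−1.04) = 0.851 (the last term is negligible), and 2 × 0.851 × 0.149 = 0.254.

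For d = 0.196: d√100 = 1.96, p = 0.50, and 2 × 0.50 × 0.50 = 0.50. This is the maximum of 2p(1 − p).

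| True change d in both groups | p | One significant, the other not |
|---|---|---|
| 0 | 0.050 | 9.5% |
| 0.1 | 0.170 | 28% |
| 0.196 | 0.500 | 50% |
| 0.28 | 0.800 | 32% |
| 0.3 | 0.851 | 25% |
| 0.5 | 0.999 | 0.2% |

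The rate falls away once the change is large enough to be significant in both groups almost always.

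**4. Can the planned data give a dose comparison?**

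Yes. The 95% CI half-width for the difference in mean change is t(0.975, 198) × √(1/n₁ + 1/n₂), in SDs of change. At 100/100 it is 1.972 × 0.1414 = 0.279. At 60/140 it is 1.972 × 0.1543 = 0.304. These ignore dropout, for which the protocol gives no figure.

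**The case against.** The strongest reply is that Section 5 must be read with Section 2. The aim already names the doses, the outcomes and the horizon, and nothing in Section 5 excludes a between-group comparison. The sentence follows directly on the follow-up item, so it may have been meant to give the assessment times. Remodeling is by nature a change within a patient, so mentioning day one and 6 months is natural. The choice of test or model may be left to an SAP that is not at hand.

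Much of this stands. A reader might infer that the trial plans no dose comparison; the documents do not support that, since the aim and the two groups show that one is intended. A reader might also infer that the groups are to be pooled; Section 5 does not say so, and separate tests in each group are an equally literal reading. Nor is the absence of a named test or model a fault here.

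What does not stand is that the sentence is merely incomplete. It is worded as the comparison to be made and it covers all data. Item H already provides for the repeat echocardiogram, so a second timing statement was hardly needed. An SAP that followed Section 5 literally would miss the aim, and one that followed the aim would depart from Section 5. The mismatch with MACE is in the text as well: items G and H suggest that few readers would attempt a day-one MACE comparison, but that leaves MACE with no stated comparison that fits it.

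**Conclusion.** Wrong as written. The only contrast that the protocol fixes for its analysis is one of time, whereas its aim is a contrast of doses, and that contrast cannot be used for MACE. This conclusion rests on the text and needs no assumed figure.

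The percentages show only what is at stake if the sentence is applied within each group: with equal doses, one significant and one non-significant change about 25% of the time at a true change of 0.3 SD, and at most 50%, reached at about 0.2 SD. They depend on the assumed 100 per group and on the assumed changes.

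The harm is limited and avoidable. The data needed for the dose comparison are already planned, and if change is reported by group with mean, SD and n, the dose difference can be derived from it.

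**What to change.** State in Section 5 that the main analysis compares the 10 mg and 25 mg groups, and give the contrast for each outcome:

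- *Echocardiographic remodeling measures:* the between-group difference at 6 months, adjusted for the day-one value of the same measure, with 95% CI.
- *MACE:* the between-group difference in 6-month incidence, or time to first event, with 95% CI.
- *Change from day one to 6 months within each group:* descriptive only, with no dose effect inferred from one group's change being significant and the other's not.

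Further model detail can stay with the SAP. The cost is one or two sentences of protocol text. No patients, visits or measurements are added, because the repeat echocardiogram and the six months of MACE follow-up are already planned.
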